## 2.2 Purpose of the Study

The purpose of the study is to show that Non-Smokers exposed to IQOS in a restaurant setting (i.e., through planned dinner “Events”) do not have higher urinary levels of Biomarkers of Exposure (BoExp) to selected HPHCs representative of ETS compared to the urinary levels of BoExp to selected HPHCs representative of ETS caused by background exposure in Non-Smokers before IQOS exposure. Furthermore the impact of passive IQOS exposure on IQOS Users and Cigarette Smokers not using any nicotine or tobacco containing nicotine product will be investigated. The addition of IQOS Users who don’t use IQOS, and Cigarette Smokers who don’t use any nicotine or tobacco products, allows for the assessment of individuals with varying levels of exposure to HPHCs in their personal lives, in order to assess whether there is any measurable additive exposure from IQOS. Relatedly, the study will also evaluate IAQ through the assessment of concentrations of selected HPHCs representative of tobacco-specific and IAQ markers in the air during the Event.

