#### 6.2.1 From Screening to Event Participation

There are no restrictions on use of IQOS or cigarettes or any other tobacco or nicotine-containing products during screening until participation in any of the events.

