6.3 Study Hypotheses And Evaluation Criteria

6.3.1 Hypotheses

There are no formal statistical hypotheses to be tested in this study. The research objective is to assess the level of BoExp to selected HPHCs representative of ETS in study participants after passive exposure to IQOS use in a restaurant setting where IQOS use, but not Cigarette smoking, is allowed.

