10 CHANGES FROM THE PROTOCOL SPECIFIED STATISTICAL ANALYSES

For the primary and secondary analysis, the random subject effect is removed as there are no repeated measures.

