12.6 Planned Statistical Analyses

12.6.1 Primary Analysis

12.6.1.1 Statistical Analysis of Primary Endpoints

For each urinary BoExp in the primary analysis NEQ, Total NNAL, Total NNN, the change between pre-event and end of study levels adjusted for creatinine will be modeled using a linear model in the Compliant Exposure Set.

The SAS procedure PROC MIXED will be used with the restricted maximum likelihood method for estimation of the parameters. The mixed model will have the change from baseline as dependent variable and the following covariates will be included in the model: Baseline, Sex, Event Type (Exposure or Non-Exposure), Duration of Exposure, Product Use Status, Product Use Status by Event Type interaction for all BoExp. In addition, an air quality covariate related to each BoExp is included in the model depending on the endpoint and is described in Appendix 15.2. This table also specifies the various IAQ covariates that are assessed using a step-wise regression approach for each BoExp. The algorithm is described below,

1. Fit a full model with all covariates

2. Drop one IAQ covariate and re-fit the model.
3. Perform a likelihood ratio test and drop the IAQ covariate with the largest p-value for the likelihood ratio statistic if it is more than 0.05.
4. Repeat steps 2 and 3 until no more IAQ covariates can be dropped.
5. Refit the final model with the IAQ covariates remaining in the model and estimate exposures for each product use group.

Appropriate contrasts will be constructed to determine the effect of passive exposure to IQOS aerosol during the Exposure Event on the mean change in levels of urinary BoExp together with the 95% CIs for non-smokers during an Exposure Event. Other contrasts can be constructed to determine the change in urinary BoExp for participants with other smoking status (Cigarette Smoker and IQOS Passive Users) after passive exposure to IQOS usage.

An example of SAS code for the final model is provided below,

```
Proc mixed data=_data_ method=reml;
Class event_type sex product_use;
Model endpoint = baseline sex event_type product_use event_type*product_use
duration <IAQ covariates> / ddfm=kr;
estimate 'Cigarette Smoker' intercept 1 baseline xx sex .5 .5 product_use 1 0 0
event type 1 event_type*product_use 1 0 0 0 0 duration xx IAQ1 xx ... IAQn xx /
alpha=0.05 cl;
Run;
```

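### The primary model pools one residual variance over Non-Smokers and abstaining product users, so users supply about half of the variance behind the Non-Smoker confidence interval

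*SAP*

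**What the plan says.** SAP 12.6.1.1 models the log-scale, creatinine-adjusted change from baseline in NEQ, Total NNAL and Total NNN. Each endpoint "will be modeled using a linear model in the Compliant Exposure Set", which holds all three groups that did not use a product. The example code declares "Class event_type sex product_use" and continues "Model endpoint = baseline sex event_type product_use event_type*product_use", followed by duration and the indoor air quality (IAQ) covariates with `ddfm=kr`. No REPEATED or RANDOM statement follows. SAP 10 explains why the protocol's random effect is gone: "For the primary and secondary analysis, the random subject effect is removed as there are no repeated measures".

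The contrast named first in 12.6.1.1 is the effect of passive exposure, with "95% CIs for non-smokers during an Exposure Event". SAP 12.6.2.2 applies a similar model to HMPMA, 3-HPMA, S-PMA and HEMA. The post-hoc models in 14.1 (Exposure versus Non-Exposure) and 14.5.1 (HeatStick consumption) keep the same variance structure. Neither document provides for group-specific variances, robust standard errors, a Non-Smoker-only fit or a residual check.

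**The concern.** With no random effect and no GROUP= option, the residual variance is the only variance parameter. Every standard error, including the one for Non-Smokers, is scaled by it. Kenward-Roger does not help, because with a single residual variance it reduces to the ordinary residual degrees of freedom.

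The documents give reasons to doubt that the groups share one variance of log change:

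- Protocol 2.2 says users are included to study "individuals with varying levels of exposure to HPHCs in their personal lives".
- For the time between screening and an event, protocol 6.2.1 states: "There are no restrictions on use of IQOS or cigarettes or any other tobacco or nicotine-containing products". Time since last use at the baseline void is therefore uncontrolled in users. Non-Smokers must have been abstinent for 12 months.
- SAP 12.1.4 replaces values below LLOQ with LLOQ/2. Where both of a participant's values are replaced, the creatinine-adjusted log change carries only the change in creatinine. This is more likely in Non-Smokers.
- SAP 7.1.2 applies a Total NNAL cutoff of 75.9 pg/mL to Non-Smokers only.

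The study is estimation only: SAP 6.3.1 says "There are no formal statistical hypotheses to be tested in this study". The intervals therefore carry the inference. An interval that is too wide makes a real increase in Non-Smokers harder to see, and one that is too narrow overstates precision.

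**Working it through.** **The plan's own figure.** The only sample-size figure is the minimum of 169 per event type (SAP 9). It cannot be reproduced, because no effect size, SD, power or precision target is given. Nothing below depends on how 169 was derived.

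**Inputs**

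- Non-Smoker share f = 0.50, tolerance ±5% (SAP Table 1), so 0.45 to 0.55.
- Nominal two-sided 95% interval, multiplier 1.96.
- r = users' SD of log change ÷ Non-Smokers' SD. This is not in the documents. It is assumed, with range 0.5 to 2 and both user groups given the same r.

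**Formulas** (Non-Smoker SD set to 1)

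- Pooled variance ≈ f + (1 − f)·r².
- Non-Smoker width ratio (pooled ÷ own) k = √(f + (1 − f)·r²).
- Non-Smoker coverage = 2Φ(1.96·k) − 1.
- User coverage = 2Φ(1.96·k/r) − 1.

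Example, r = 2: k = √(0.5 + 0.5·4) = √2.5 = 1.581. Non-Smoker coverage is 2Φ(3.10) − 1 = 99.8%. For users, k/r = 0.791, which gives 87.9%.

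| r | k | Non-Smoker coverage | User coverage |
|---|---|---|---|
| 0.5 | 0.791 | 87.9% | 99.8% |
| 0.67 | 0.851 | 90.5% | 98.7% |
| 0.8 | 0.906 | 92.4% | 97.3% |
| 1 | 1.000 | 95.0% | 95.0% |
| 1.25 | 1.132 | 97.3% | 92.4% |
| 1.5 | 1.275 | 98.8% | 90.4% |
| 2 | 1.581 | 99.8% | 87.9% |

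At the edges of the mix tolerance, Non-Smoker coverage at r = 0.5 is 86.7% (f = 0.45) to 88.9% (f = 0.55). At r = 2 it is 99.9% to 99.7%.

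**Simulation check.** The SAP model without IAQ covariates was simulated with 84 Non-Smokers, 42 Cigarette Smokers and 43 IQOS Passive Users per event type, 4,000 runs per r. For r = 0.5, 0.67, 1, 1.5 and 2:

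- Non-Smoker coverage at Exposure Events: 88.6%, 90.2%, 94.9%, 98.7%, 99.8%.
- Non-Smoker Exposure versus Non-Exposure contrast (as in 14.1): 88.3%, 91.0%, 94.8%, 98.9%, 99.8%.

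**Does the remedy work?** A Non-Smoker-only fit gave 95.0% to 95.2% coverage for the Exposure Event estimate at every r. A separate simulation with group-specific residual variances gave 94.2% to 95.9% for every contrast and every r. At r = 1 the width ratio was 0.999, so almost nothing is lost if the variances are in fact equal.

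**The case against.** The case for leaving the model alone has substance. A common-variance linear model on log data is conventional. Taking logs is a standard variance-stabilising step, and the model also adjusts for baseline. Groups that differ in level of exposure need not differ in the SD of log change. That stands: the documents show unequal variances to be plausible, not actual, and at r between 0.9 and 1.1 Non-Smoker coverage is 93.8% to 96.1%, which is harmless.

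No test, margin or success rule depends on the interval. That also stands, and it limits the consequence to interval width.

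SAP 12.6.1.2 already plans summaries of change by product use and event type, with SD and 95% CI. These let a reader see the spread in each group, but they are unadjusted and do not replace the model-based estimate. SAP 12.1.4 also withholds such statistics when 50% or more of the data are below LLOQ, which is a case where group spread would matter.

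Group-specific variances have a weakness of their own. If many Non-Smoker values are imputed, the Non-Smoker variance will partly describe imputation and creatinine, and the interval could look falsely precise. This is a reason to report the share below LLOQ beside the result. It does not justify borrowing the users' variance.

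Two stronger readings are tempting, and the documents support neither. One is that the Non-Smoker interval reflects the users' spread; it reflects a mixture to which Non-Smokers contribute about half. The other is that the interval is too wide and so hides an increase. That needs r above 1, and no group SD is given.

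**Conclusion.** The point holds as a structural one: the models as written assume equal residual variances across three groups whose changes arise from different processes, and neither document justifies or checks this. If the variances differ, either the Non-Smoker or the user intervals undercover, and which of them depends on the unknown r. Over the assumed range 0.5 to 2, Non-Smoker coverage runs from about 88% to 99.8%, with user coverage mirrored. If r is near 1 the issue disappears. The pooling does not bias the point estimates.

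The figures rest on the 50/25/25 mix, one common r for both user groups, and a simulation without IAQ covariates. This is an inexpensive improvement to the precision statement for the main Non-Smoker estimate, not a demonstrated error in it.

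**What to change.** Add `repeated / group=product_use;`, keeping `ddfm=kr`, to the models in SAP 12.6.1.1, 12.6.2.2, 14.1 and 14.5.1. Report the estimated residual variance for each product-use group with each endpoint, and beside it the share of values below LLOQ in that group; 12.1.4 already requires the counts.

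SAP 14.1 shows that primary results had been reviewed before the post-hoc section was written. If the change is made after that review, present it as a labelled additional analysis next to the planned model, not as a replacement.

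The cost is one line of code per model and two more variance parameters. No new data are needed, and the loss is negligible if the variances are equal. The change does not deal with correlation from participants who attend both a Non-Exposure and an Exposure Event, which needs separate treatment.

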12.6.1.2 Descriptive Analysis and Listing of Primary Endpoints

The level of BoExp parameters (NEQ, Total NNAL, Total NNN) and their change from Baseline will be summarized by Product Use Status (Non-Smoker, IQOS Passive User, Cigarette User), Event Type (Exposure vs Non-Exposure) and sex for the Compliant Exposure Set. All BoExp values will be log-transformed (base_e) prior to the analysis.

For each BoExp parameter, the quantity excreted at baseline and from last urine void together with the change from baseline (both relative change and absolute change) will be summarized according to descriptive statistics listed in Section 12.1.2. In addition, the concentrations adjusted for creatinine and also its change from baseline will be summarized in a similar fashion.

Line graphs with the geometric means for each parameter and 95% CI over time (baseline and last void) will be produced. In each graph, the values of both Exposure and Non-Exposure Events for each Product Use Status will be plotted. The same graph will be repeated stratified further using sex.

12.6.2 Secondary Analysis

12.6.2.1 Indoor Air Quality Assessment

The assessment of the various IAQ compounds between Exposure and Non-Exposure Events will be analysed using a mixed model approach. The precise definition of each endpoint is detailed in Section 8.2.2.

12.6.2.1.1 Carbonyls

During each Exposure and Non-Exposure Event, there are 3 sampling cases that collects air for the assessment of carbonyls at 1 hour intervals. Each sampling case was placed at the same location during an Event.

The SAS procedure PROC MIXED will be used with the restricted maximum likelihood method for estimation of the parameters. The mixed model will have the carbonyl reading as dependent variable and the following covariates will be included in the model: Location, Event Number (Exposure Events 1-4 and Non-Exposure Event 1 and 2) and Event Type (Exposure and Non-Exposure Event). A repeated statement will be used to model repeated measures for the time variable.

The denominator degrees of freedom will be determined using the method of Kenward and Roger (1997). In case of non-convergence of the preferred model or memory space issues, the Kenward-Roger method will be replaced by Satterthwaite approximation.

The SAS code for the mixed model to be used is shown below:

```
Proc mixed data=_data_ method=reml;
Class location time event_type;
Model endpoint = location event type event num/ ddfm=kr;
Repeated time/subject=location(event num) type=cs;
Lsmeans event_type / diff alpha=0.05 cl;
Lsmeans location / diff alpha=0.05 cl;
Run;
```

The Geometric LS means and estimate of the ratio of geometric means between Exposure and Non-Exposure Events along with its 95% CI will be presented in tables for Formaldehyde, Acetaldehyde, Acrolein and Crotonaldehyde. The geometric LS means and ratio of geometric means together with their respective CIs are calculated by exponentiating the LSmeans and differences between exposures groups.

12.6.2.1.2 Tobacco-specific markers and Tobacco-specific nitrosamines

During each Exposure and Non-Exposure Event, there are 3 sampling cases that collects air for the assessment of Tobacco-specific markers (3-Ethynylpyridine (3-EP) and Nicotine) and Tobacco-specific nitrosamines (NNN and NNK) at 3 hour intervals. For each sampling case it was placed at the same location during an event, each sampling case provides two replicates.

The SAS procedure PROC MIXED will be used with the restricted maximum likelihood method for estimation of the parameters. The mixed model will have the value of the exposure as dependent variable and the following covariates will be included in the model: Location, Event Number (Exposure Events 1-4 and Non-Exposure Event 1 and 2) and Event Type (Exposure and Non-Exposure Event). Replicate will be modelled as a repeated variable.

The denominator degrees will be the same as describe for the Carbonyls (Section 11.6.2.1.1).

The SAS code for the mixed model to be used is shown below:

```
Proc mixed data=_data_ method=reml;
  Class location replicate event_type;
  Model endpoint = location event_type/ ddfm=kr;
  repeated replicate /subject=location(event_type) type=cs;
  Lsmeans event_type / diff alpha=0.05 cl;
  Lsmeans location / diff alpha=0.05 cl;
Run;
```

The Geometric LS means and ratio of geometric means between Exposure and Non-Exposure Group along with its 95% CI will be presented in tables for Nicotine, 3-ethenylpyridine, NNN and NNK. The geometric LS means and ratio of geometric means together with their respective CIs are calculated by exponentiating the LSmeans and differences between exposures groups.

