12.6.2.1.3 Particles Suspended in Air

During each Exposure and Non-Exposure Event, there are 2 Dust Trak sensors that measure in real-time suspended particulate matter in air (PM1, PM2.5, PM4 and PM10) every minute. Each sensor was placed at different locations during an event. To assess the change in particulate matter suspended in air between an Exposure and Non-Exposure Event, this will be modelled using a linear model.

The SAS procedure PROC MIXED will be used with the restricted maximum likelihood method for estimation of the parameters. The dependent variable will be the average of the 1 minute readings from the start till end of each event for each sensor. The mixed model will use the mean as dependent variable and the following covariates will be included in the model: location and event type.

The denominator degrees will be the same as describe for the Carbonyls (Section 11.6.2.1.1).

The SAS code for the mixed model to be used is shown below:

```
Proc mixed data=_data_ method=reml;
  Class location event_type;
  Model endpoint = location event_type/ ddfm=kr;
  Lsmeans event_type / diff alpha=0.05 cl;
  Lsmeans location/ diff alpha=0.05 cl;
Run;
```

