14.4 Additional Secondary Analysis on IAQ Parameters Performed by CRO

During the review and finalization of the results from the secondary analysis of the IAQ parameters it was identified that there was a discrepancy between the SAP specified model and the results provided by the CRO [REDACTED]. The planned model, uses observations collected at each timepoint for each events in the model however [REDACTED] used a model with endpoints averaging observations from each event.

This was due to an incorrect model specification in section 11.6.2.1.1. which did not allow the specified model to converge. Results from this additional analysis will be kept and presented in the Appendix of the study report.

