14.6 Additional Analysis to Account for Pre-Event Levels of IAQ Parameters

The review of the pre-event IAQ data described in section 14.3 suggests that the levels of building background should be taken into account during the statistical analysis of the IAQ parameters. The statistical analysis of IAQ parameters described in sections 12.6.2.1.1, 12.6.2.1.2 and 12.6.2.1.3 will therefore be repeated but the endpoint will be the change from pre-event average instead of the raw values measured during an event. Note that the change from pre-event average will be log-transformed prior to analysis. The estimates from these models will be exponentiated and reported as geometric means for each Event type. Comparisons between Exposure and Non-Exposure Event will be reported as ratio of geometric means. All estimates will be reported together with their corresponding 95% confidence intervals.

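### The indoor-air models have no between-event variance term although event type varies over only six Events, so Exposure versus Non-Exposure intervals can be too narrow

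*SAP*

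**What the plan says.** SAP 12.6.2.1 compares air quality between Exposure and Non-Exposure Events with three models, each reporting the event-type difference or ratio with a 95% confidence interval.

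- **Carbonyls (12.6.2.1.1).** The text lists "Location, Event Number (Exposure Events 1-4 and Non-Exposure Event 1 and 2) and Event Type" as covariates. The code has "Model endpoint = location event type event num/ ddfm=kr" and "Repeated time/subject=location(event num) type=cs". Event number is not in the CLASS statement.
- **Nicotine, 3-EP, NNN and NNK (12.6.2.1.2).** The text lists the same covariates, but the code drops event number from the model and uses "repeated replicate /subject=location(event_type) type=cs".
- **Particles (12.6.2.1.3).** Each sensor gives one average per Event, and "the following covariates will be included in the model: location and event type". There is no RANDOM or REPEATED statement.

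Three later sections bear on this. Section 14.4 reports that the CRO averaged readings by Event: "This was due to an incorrect model specification in section 11.6.2.1.1. which did not allow the specified model to converge". It adds: "Results from this additional analysis will be kept and presented in the Appendix of the study report". Section 14.2 adds post-hoc models that work at event level, for carbonyls only. Section 14.6 says that review of the pre-event data "suggests that the levels of building background should be taken into account during the statistical analysis of the IAQ parameters", and repeats the three planned models on change from the pre-event mean, with no event term added.

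**The concern.** The unit that carries event type is the dinner, so the comparison rests on four units against two. Cases in one room on one evening share the same outdoor air, attendance, cooking and consumption. A model that treats them as independent, given location and event type, counts the same evening two or three times.

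Listing event number as a fixed covariate does not help. Outside CLASS, as coded, it is a straight line beside event type. Inside CLASS, it would absorb event type completely.

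The design holds the restaurant, ventilation and menu constant (SAP 7.1.3), but the SAP itself expects dinners to differ: 14.2 models food and alcohol consumed, and 14.6 asks for background to be considered. Air quality is the first secondary objective. An understated standard error could present an ordinary difference between evenings as an effect of IQOS, or present similarity with false precision.

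**Working it through.** **Inputs from the documents.** Six Events, four Exposure and two Non-Exposure (SAP 12.6.2.1.1). Readings per Event (SAP 8.2.2): carbonyls 3 cases × 3 hours = 9; markers and nitrosamines 3 cases × 2 replicates = 6; particles 2 sensor averages. The 9 and the 6 match the SAP's own counts. Over six Events this gives 54, 36 and 12 observations. Intervals are two-sided 95%.

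**Assumption.** The documents give no between-event variance. Let *s* be the share of the variance of a location-by-event mean that is common to the Event. Total variance is set to 1, so widths are in SDs of that mean.

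**Three cases per Event, location within Event as subject.** An event mean has variance s + (1−s)/3 = (1+2s)/3. The true variance of the event-type contrast is (1/4 + 1/2)(1+2s)/3 = 0.25(1+2s). A model with location and event type only has expected residual mean square [4(1+2s) + 10(1−s)]/14 = 1 − s/7, and so reports 0.25(1 − s/7). True over reported variance is (1+2s)/(1 − s/7): 1.5/0.964 = 1.56 at s = 25%, and 2/0.929 = 2.15 at 50%.

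**Particles, two sensors.** The same steps give (1+s)/(1 − s/9): 1.25/0.972 = 1.29 at 25%, and 1.5/0.944 = 1.59 at 50%.

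**Marker code as written.** Read as compound symmetry over all readings of a location-by-type subject, its standard error comes from how the Exposure minus Non-Exposure difference varies over three locations (about 2 df). Event effects common to all locations cancel from that variation, so the reported variance is 0.25(1−s). The ratio is (1+2s)/(1−s): 1.5/0.75 = 2 at 25%, and 2/0.5 = 4 at 50%.

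**Event number in the carbonyl model.** As a straight line it raises the contrast's variance multiplier from 0.25 to 0.7955 (×3.2) if Events are numbered 1–6 with Non-Exposure first, or to 0.3106 (×1.2) if numbered within type. As a CLASS factor it gives rank 6 with or without event type, so the event-type difference is not estimable. With within-type numbering, `location(event num)` would also put an Exposure and a Non-Exposure dinner in one subject.

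**Simulated error of a nominal 5% comparison (%), no true difference:**

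| Assumed share s | 0 | 10% | 25% | 50% | 75% |
|---|---|---|---|---|---|
| Carbonyls, numeric event number (13 df) | 4.9 | 7.4 | 11.7 | 19.3 | 27.9 |
| Particles (9 df) | 4.9 | 6.0 | 7.9 | 11.5 | 15.5 |
| Markers, subject corrected to location within Event (14 df) | 4.9 | 7.2 | 10.9 | 17.4 | 24.4 |
| Marker code as written, unconstrained (2 df) | 5.0 | 6.6 | 9.4 | 16.4 | 30.8 |
| Six event means (4 df) | 5 | 5 | 5 | 5 | 5 |

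The carbonyl row takes each location-by-event as its own subject; either numbering gives nearly the same error. The marker code depends on how the covariance boundary is handled: 1–7% at shares of 0–10%, 4–9% at 25%, 10–16% at 50% and 21–31% at 75%.

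**Mean half-width (SD) at the same shares.** Marker code as written: 1.9/1.8/1.7/1.4/1.0. Event means: 1.3/1.4/1.6/1.9/2.1. The coded interval shrinks as dinners differ more.

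**Cross-check with separate replicate variance.** Here the share ρ refers to a single reading, with the rest split equally between case and replicate. For markers, ρ = 0.3 corresponds to s = 0.3/(0.3 + 0.35 + 0.175) = 0.36. Coverage of the 95% interval at ρ = 0/0.1/0.3/0.5/0.8 was:

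- carbonyls: 95/92/83/78/68%
- particles: 95/94/92/89/84%
- marker code: 98/97/94/87/73%, or 95/91/86/77/61% with the compound-symmetry covariance held at or above zero
- event means: 94.5–95.5% throughout

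**Random-event model.** Error stays at 3–5% at every share. The event variance is estimated as zero in 42/26/10/2% of runs at s = 10/25/50/75% with three cases, and in 44/32/15/4% with two sensors.

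**The case against.** - **The size is assumed.** This stands: no document gives a between-event variance. At s = 0 nothing is inflated, and particle error at 10–25% is only 6.0–7.9%.
- **Some coded intervals are not narrow.** This stands at low shares. The marker interval is wider than the event-level one up to about s = 25%. For carbonyls numbered 1–6, the half-width at 25% is 1.81 SD against 1.60 SD for event means, because the event-number line inflates the variance. Yet error there is still 11.7%: the interval is too narrow for the estimator it accompanies.
- **The code is only illustrative.** The revision history calls these blocks pseudo code, and nothing was run in SAS. Replicate levels recur within a marker subject, so that code may not run as written, but this is untested. The missing event variance does not depend on it: no model's text or code contains such a term.
- **The failure in 14.4 may concern superseded code.** Possible, since version 2.0 updated the carbonyl block and also added the post-hoc section. The current block still has no event variance.
- **The remedy already exists.** Partly true. Table 15.2.2.7.4 is an event-averaged analysis whose title is not limited to carbonyls. But 14.4 sends it to the report appendix, and 14.6 reruns the planned models. Subtracting a pre-event mean removes background that is stable through an evening, not variation arising during dinner.
- **There are no formal hypotheses.** True of the study, but each model reports a 95% interval, and Protocol 12.5 sets a 0.05 level for judging equality between air-quality sessions.

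**Conclusion.** The concern holds. The planned models leave between-event variation out of the event-type standard error, and nothing in SAP section 14 replaces them. Under-coverage becomes visible once Events hold roughly 10% or more of the variance of a location-by-event mean. At 25% the nominal 5% error is about 12% for carbonyls, 8% for particles and 4–9% for the marker code as written. At 50% the figures are about 19%, 11% and 10–16%.

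These sizes rest on the assumed share, on normal errors with balanced readings, on each carbonyl location-by-event being its own subject, and on the marker code being read as compound symmetry over the subject. The count of six Events is the SAP's; Protocol Table 5 shows five. The point affects the first secondary objective and should be corrected.

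**What to change.** In SAP 12.6.2.1.1 to 12.6.2.1.3, and in the repeat under 14.6:

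- Put a unique event identifier (1–6) in CLASS, remove event number from the fixed effects, and add `random event(event_type);`.
- In the carbonyl and marker/nitrosamine models, use `subject=location(event)` in the REPEATED statement. The particle model needs only the random event term.
- Keep Kenward-Roger degrees of freedom.
- Because six Events will sometimes give a zero event variance, report the event-averaged comparison (six means, 4 df) beside the model in the main tables.
- Align text and code, and label the change as a post-hoc correction, since 14.1, 14.4 and 14.6 show that results or pre-event data had already been reviewed.

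The cost is a few lines of code, matching text and one rerun on existing data. At an assumed 25% share, the mean half-width goes from 1.33 to 1.79 SD for particles, and from 1.03 to 1.60 SD for markers measured against the subject-corrected model. Against the marker code as written (about 1.7 SD), or carbonyls numbered 1–6 (1.81 SD), the interval at that share would be slightly narrower. About 4 df is what six Events can support.

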8.2.2 Secondary Analysis of Indoor Air Quality Measurements

- Carbonyls: Acetaldehyde, Acrolein, Crotonaldehyde and Formaldehyde
 - At each event there are 3 suitcases sampling each sample at 1 hour intervals over 3 hours.
 - Each of the 9 observations will be used as the observations for the associated event.
- ISO measurement standards for ETS: 3-Ethenylpyridine (3-EP) and Nicotine
 - At each event there are 3 suitcases sampling 2 replicate samples at the end of the 3 hour interval.
 - Each of the 6 observations will be used as the observations for the associated event.
- Tobacco Specific Nitrosamines: NNN and NNK
 - At each event there are 3 suitcases sampling 2 replicate samples at the end of the 3 hour interval.
 - Each of the 6 observations will be used as the observations for the associated event.

- Real-time measurements of PM2.5 and PM10 suspended particles in air.
 - At each event there are 2 sensors measuring the suspended particulate matter a 1 minute interval monitoring.
 - For each sensors, the average of all readings will be calculated from the start till end of the event. These averages will be used as observations for that particular event.

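### The nicotine, 3-EP, NNN and NNK air model has no event identifier, so its repeated-measures code merges evenings and, with replicates coded 1/2, cannot be fitted

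*SAP*

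**What the plan says.** SAP 12.6.2.1.2 analyses nicotine, 3-EP, NNN and NNK in air, all endpoints of the first secondary objective. Of each case the prose says that "it was placed at the same location during an event, each sampling case provides two replicates", and then "Replicate will be modelled as a repeated variable". SAP 8.2.2 gives three cases with two replicates each: "Each of the 6 observations will be used as the observations for the associated event". The covariates named in the prose are location, "Event Number (Exposure Events 1-4 and Non-Exposure Event 1 and 2) and Event Type".

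The code differs from this. Its class line is "Class location replicate event_type", its model line is "Model endpoint = location event_type/ ddfm=kr", and its covariance line is "repeated replicate /subject=location(event_type) type=cs". Event number appears in none of the three, and there is no RANDOM statement. The neighbouring carbonyl model (SAP 12.6.2.1.1) does nest location within event number. SAP 14.6 repeats the 12.6.2.1.2 analysis on change from the pre-event average and does not alter the specification.

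**The concern.** The subject option tells the procedure which readings belong together. The prose pairs the two replicates of one case on one evening. The code instead joins every evening of the same type at a location into one unit, and within that unit the repeated effect has only two levels to tell the readings apart.

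This puts the Exposure/Non-Exposure comparison of the four tobacco-specific air constituents at risk. Either the model fails and the analyst has to improvise after seeing data, or it runs with a cluster that does not match the sampling and gives an interval of unknown quality.

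**Working it through.** **Inputs.** From SAP 8.2.2: 3 cases and 2 replicates per event. From SAP 12.6.2.1.2: 4 Exposure and 2 Non-Exposure Events, and the printed code. The documents give no variances, so every variance share below is an assumption.

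**1. Reproduce the plan's count.** 3 cases × 2 replicates = 6 readings per event, as SAP 8.2.2 states. Over six events this is 36 readings. The units that the prose describes number 3 × 6 = 18, with 2 readings each.

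**2. Units formed by the code.** Location within event type gives 3 × 2 = 6 subjects. Three hold 4 evenings × 2 = 8 readings and three hold 2 evenings × 2 = 4 readings (24 + 12 = 36).

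**3. Rank of the covariance block.** With replicate coded 1/2, the compound-symmetry matrix C is 2 × 2. A subject's block is R = Z C Zᵀ, where Z has one row per reading and two columns. Its rank cannot exceed 2. Built numerically, the blocks have rank 2 of 8 and 2 of 4, with smallest eigenvalue 0. With no RANDOM statement the total covariance is R itself, so its inverse and log-determinant, which REML needs, do not exist. With the three Exposure Events of Protocol Table 5, the Exposure block would be rank 2 of 6, still singular.

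**4. Partial repairs that do not work.**
- Adding Event Number as a categorical fixed effect with six levels: location plus event has rank 8, and adding event type leaves it at 8. The event-type difference is not estimable.
- Adding a random event effect but keeping the printed REPEATED line: the total covariance has rank at most 6 × 2 + 6 = 18 of 36, so it is still singular.

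**5. Versions that run.** The table gives simulated coverage of the nominal 95% CI for the event-type difference, from 2,500 runs per column. Total variance is 1. The assumed case-by-evening share is 0.2 (0.1 in the last column), and the remainder is replicate error. The true SE of the difference is √[(evening + case/3 + replicate/6) × (1/4 + 1/2)]. For an evening share of 0.50 this is √[(0.50 + 0.0667 + 0.05) × 0.75] = 0.68.

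| Assumed evening share | 0 | 0.10 | 0.25 | 0.50 | 0.75 |
|---|---|---|---|---|---|
| True SE | 0.39 | 0.46 | 0.55 | 0.68 | 0.78 |
| Printed subject, unique replicate codes, covariance unbounded, about 2 df | 99.1% | 97.6% | 94.6% | 87.9% | 77.2% |
| Same, covariance held at or above 0, median 32 df | 95.6% | 92.0% | 86.4% | 76.5% | 62.9% |
| Subject = location within event, no event effect, 14 df | 95.1% | 91.0% | 85.9% | 80.2% | 74.2% |
| Event as the unit, 4 df | 94.6% | 94.2% | 94.8% | 95.1% | 95.0% |

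At an evening share of 0.50, the printed subject (about 2 df) gives a root-mean-square model SE of 0.31 against the true 0.68. Only the last row holds its level throughout.

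**The case against.** The strongest reply is that this is a slip in sample code. The prose names Event Number and the carbonyl code nests location within it, so a competent programmer would add the identifier. That may well happen, but the prose gives it as a fixed covariate, which makes event type inestimable if it is entered as a six-level factor. Adding it only to the subject leaves evening variance out. The plan does not lead to a workable model by itself. The revision history records an update to this code in version 2.0, but the text under review still has the problem.

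A second reply is that replicate coding is not defined, and codes unique across evenings would avoid the singularity. This stands: failure to fit is conditional on 1/2 coding, which is what two replicates per case suggests.

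A third is that an event-averaged analysis already exists. SAP 14.4 keeps one for the appendix, and the title in the table list is not confined to carbonyls. But the only misspecification that 14.4 names is in the carbonyl section, and it presents the averaged results as additional. A reader might infer from 14.4 that the present model has already failed and been replaced; the text does not say so.

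A reader might also infer that the carbonyl model is singular. That requires event numbers to restart within event type in the data set. The SAP's labels could be read that way, "Event Number (Exposure Events 1-4 and Non-Exposure Event 1 and 2", but Protocol Table 5 numbers events consecutively across types, so the documents do not establish it.

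**Conclusion.** The code contradicts the prose. With replicate coded 1/2, the planned ratio and CI for nicotine, 3-EP, NNN and NNK cannot be obtained. That result rests on counting and matrix rank and needs no variance assumption. It was derived from how the REPEATED effect indexes the covariance matrix and was not run in SAS.

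With unique codes the model runs on the wrong cluster. It would be tempting to attach one false-positive rate to this, or to say that the interval is always too narrow. The documents support neither: in the table the about-2-df version is conservative with no evening variance, near nominal at a share of about 0.25 and too narrow above that. It would be equally tempting to treat location within event as the whole cure; it is valid only if evenings do not differ.

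The reach is limited to secondary air endpoints in a study without formal hypotheses. The primary urinary models use different code. The correction should be made, including for the repeat analysis in SAP 14.6.

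**What to change.** In SAP 12.6.2.1.2:
- Define an event identifier with six distinct values and put it in CLASS.
- Keep location and event type as the fixed effects, and remove Event Number from the fixed covariates in the prose.
- Add `random event;` and write `repeated replicate / subject=location(event) type=cs;`.
- Alternatively, analyse the six event means, which leaves 6 − 2 = 4 df for event type. In this balanced layout the two agree unless the event variance estimate is held at zero, so state in advance how that case is handled.

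Use the same specification in SAP 14.6. Use the same identifier in the carbonyl model, as a precaution, so that events of different types cannot share a subject.

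The change needs no new data. Its cost is precision: with about 4 df the interval will usually be wider. At an assumed evening share of 0.50, the median width is 3.47 with event as the unit, against 1.79 with the subject option alone changed and 2.21 with the printed subject and unique codes (about 2 df). With no evening variance the figures are 1.95, 1.61 and 2.75. The extra width at the larger share reflects having only six evenings to compare.
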